#### **INTRODUCTION**

The aim of this Statistical Analysis Plan (SAP) is to describe an analytic and solid framework that will be followed in order the final efficacy analysis of the ALERT-lung trial to be implemented. A short description of the contents of this statistical analysis plan is provided below:

- 1. **Trial oversight**: trial's schema, objectives and trial endpoints, eligibility criteria, study treatment, statistical design (sample size and power), trial duration
- 2. **Statistical considerations for final analysis**: analysis timing, definition of primary and secondary endpoints, (serious) adverse events definition, analysis populations
- 3. Primary efficacy analysis of alectinib in terms of best overall response (OR) assessed by RECIST v1.1
- 4. **Additional secondary analysis:** accrual and baseline characteristics, follow-up and treatment administration, secondary analysis (including analysis of biomarkers available)
- 5. Technical issues: data retrieval, testing, handling of missing data, reporting conventions

# 1 Trial oversight (according to trial protocol)

ALERT-lung is a single arm, multicentre phase II trial evaluating the activity of alectinib as second-line treatment of pretreated RET-rearranged advanced NSCLC.

# treatment may continue beyond progression if there is clinical benefit

# 1.1 Objectives

#### Primary objective

The **primary objective** is to assess the efficacy of alectinib in terms of best overall response (OR) assessed by RECIST 1.1., from the start of trial treatment across all time points until the end of trial treatment.

#### Secondary objectives

The **secondary objectives** of the study include:

- To evaluate secondary measures of clinical efficacy including disease control, progressionfree survival (PFS), and overall survival (OS).
- To assess the safety and tolerability of the treatment.

#### Correlative studies

Further exploratory analyses include description of primary and secondary outcomes for patient subgroups of interest, as defined by patient or tumour characteristics or different levels of biomarkers examined.

#### 1.2 Endpoints

#### Primary endpoint:

• Best overall response (OR = CR or PR), per investigator assessment, according to RECIST 1.1.

#### Secondary endpoints:

- Best overall response per independent review.
- Disease control at 24-weeks: best overall response of CR or PR, or SD (or non-CR/non-PD in the case of non-measurable disease only)
- PFS defined as the time from the date of enrolment until documented progression or death, if progression is not documented
- OS defined as time from the date of enrolment until death from any cause
- Safety and tolerability

#### 1.3 Most important eligibility criteria

#### Inclusion criteria:

- Histologically or cytologically documented non-small cell lung carcinoma.
- Advanced disease defined as recurrent stage IV (according to 8th TNM classification) or recurrent or progressive disease following multimodal therapy (radiation therapy, surgical resection, or definitive chemo-radiation therapy for locally advanced disease).
- At least one prior platinum-based systemic regimen: Adjuvant or neoadjuvant or definitive platinum-based chemo-radiotherapy treatments are considered as a line of treatment only if completed less than 6 months before enrolment. Maintenance therapy following platinum doublet-based chemotherapy is not considered a separate regimen of therapy.
- RET rearrangement detected by FISH, Nanostring or by parallel-sequencing on FFPE tumour tissue assessed locally.
- Availability of FFPE tumour material for central confirmation of RET-rearrangement.
- Measurable or non-measurable, but radiologically evaluable (except for skin lesions) disease according to RECIST v1.1 criteria.

- Age ≥18 years.
- Eastern Cooperative Oncology Group (ECOG) Performance Status 0-2.
- Life expectancy >3 months.

#### Exclusion criteria:

- Untreated, active CNS metastases.
- Carcinomatous meningitis.
- Any previous (in the past 3 years) or concomitant malignancy EXCEPT adequately treated basal or squamous cell carcinoma of the skin, in situ carcinoma of the cervix or bladder, in situ ductal carcinoma of the breast.
- Any serious diseases or clinical conditions, including but not limited to uncontrolled active infection and any other serious underlying medical processes, that could affect the patient's capacity to participate in the trial.
- Previous treatment with any RET TKI or RET targeted therapy.
- Patient with locally detected EGFR, ROS or ALK mutation (in addition to RET rearrangement).
- Any concurrent systemic anticancer therapy.
- Women who are pregnant or in the period of lactation.

#### **1.4 Trial treatment**

Alectinib is administered orally, 600 mg, twice per day (1200 mg per day) until progression, refusal or unacceptable toxicity. Trial treatment may also continue beyond progression, with physician and patient agreement, for as long as the patient may still derive clinical benefit as per investigator decision. Treatment has to start as soon as possible after enrolment, ideally within 7 days. Treatment visits are planned at treatment start (week 0) and then every 2 weeks (±3 days) for the first 12 weeks and every 4 weeks (±3 days) thereafter.

#### 1.5 Statistical design, sample size & power

According to the protocol, the trial targets a best OR rate of 35% and considers an OR rate of 15% as too low.

Based on a one-sided exact test for proportions, the trial is designed to test the following hypotheses: H0: p0 ≤0.15 vs HA: pA>0.35, where p is the rate of best OR (ORR) at a one-sided significance level of 0.025 and a power of at least 0.80.

A significance level of 0.015 and power of 0.82 are achieved with a sample size of 41 evaluable patients. The null hypothesis will be rejected and the alternative hypothesis accepted if at least 12 patients achieve OR.

The total sample size of **44 patients** allows for up to 3 patients to be replaced if a patient is ineligible (retrospective review), has not started the experimental treatment or is lost to follow-up before evaluation of response.

#### **1.6 Total trial duration**

Clinical visits are expected to span approximately **44 months** after enrolment of the first patient. Assuming an accrual rate of approximately 1 patient per month and a start-up period of 6 months as the trial is activated by participating centres, the final trial report is expected to be available approximately 5 years after the enrolment of the first patient.

# 2 Statistical considerations for final analysis

### 2.1 Premature trial closure

Since the activation of the ALERT-lung trial in April 2018, promising new agents for the treatment of RET-rearranged NSCLC have been introduced. At the same time, in a Japanese study, alectinib has shown only moderate activity in this indication.

For both the aforementioned reasons, **ETOP decided to prematurely close the ALERT-lung trial, by March 31, 2021.** Follow-up and safety information will be updated until 31 March 2021.

A final analysis will be performed based on all enrolled patients and respective available information collected up to trial's premature closure.

#### 2.2 Study's endpoints

#### 2.2.1 Primary endpoint

Overall response (OR) is defined as best overall response (complete response (CR) or partial response (PR) according to RECIST criteria v1.1 from the start of trial treatment across all time points until the end of trial treatment.

Objective response rate (ORR) will be calculated as the rate of patients achieving CR or PR over the total number of patients in the analysis cohort.

#### 2.2.2 Secondary endpoints

Secondary endpoints, according to the protocol, include disease control at 24-weeks, PFS, OS, safety and tolerability. More specifically:

- Disease control (DC) is defined as complete or partial response, or disease stabilisation at 24 weeks. Accordingly, disease control rate (DCR) will be calculated as the rate of patients achieving DC over the total number of patients in the analysis cohort.
- PFS is defined as the time from the date of enrolment until documented progression (based on RECIST 1.1 criteria) or death, if progression is not documented. Censoring (for patients without a PFS/death event) will occur at the date of last tumour assessment if patient is lost to follow-up or refuses further documentation of follow-up.
- OS is defined as time from the date of enrolment until death from any cause. Censoring will occur at the last follow-up date.

All safety parameters will be summarised in tables to evaluate the safety profile of patients treated with alectinib in terms of:

- Adverse events including adverse events leading to dose modifications or interruptions, study drug withdrawal, and death
- Any cause adverse events; Treatment-related adverse events
- Severe, serious, and selected adverse events
- Deaths
- Laboratory parameters and abnormalities, vital signs and ECGs

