# 2.3 Analysis populations

**Intention-To-Treat Cohort:** The Intention-To-Treat (ITT) cohort will include all patients enrolled in the trial.

**Efficacy Cohort:** The efficacy cohort will encompass all evaluable patients, i.e., all enrolled patients excluding patients that were found to be ineligible (in retrospective review), patients that have never started the trial treatment and patients that are lost to follow-up before their first response evaluation (by RECIST 1.1).

**Safety Cohort:** The safety cohort will include all enrolled patients that have received at least one dose of trial treatment.

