## 4.3 Secondary and exploratory efficacy endpoints

#### 4.3.1 Disease control rate

**Clinical efficacy** will be further explored by the estimation of **disease control rate (DCR) in the efficacy cohort**.

- Disease control rate (DCR) at 24 weeks will be presented along with its 95% exact binomial CI.
- The use of univariate and multivariate logistic regression models will be considered (if possible, taking into account the limited number of enrolled patients) to investigate the effect of the clinicopathological variables of interest (gender, age category, smoking history, ECOG performance status at enrolment, and stage at enrolment) on DCR.

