#### 5.1 Data Retrieval Information

On February 8, 2021, ETOP announced the premature closure of the ALERT-lung trial (ETOP 12-17 ALERT-lung Trial Closure Guidance Letter). **Trial will be terminated by March 31, 2021**. **Follow-up and safety information will be updated until March 31. All outstanding data and query replies will be submitted by 28 February 2021. Final database lock and trial closure date will be on 31 March 2021**.

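### The 24-week disease control rate keeps the whole cohort as denominator after an administrative stop, with no rule for patients who could not reach week 24; if there are any, the rate is pulled downward

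*SAP*

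**What the plan says.** Section 2.2.2 defines the endpoint at a fixed time: "Disease control (DC) is defined as complete or partial response, or disease stabilisation at 24 weeks". It then sets the denominator: "disease control rate (DCR) will be calculated as the rate of patients achieving DC over the total number of patients in the analysis cohort". Section 1.2 words the same endpoint differently, as "Disease control at 24-weeks: best overall response of CR or PR, or SD".

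Section 4.3.1 places the analysis in the efficacy cohort: "Disease control rate (DCR) at 24 weeks will be presented along with its 95% exact binomial CI".

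On the early stop, section 2.1 says "Follow-up and safety information will be updated until 31 March 2021" and "A final analysis will be performed based on all enrolled patients and respective available information collected up to trial's premature closure". Section 5.1 adds an earlier deadline: "All outstanding data and query replies will be submitted by 28 February 2021".

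The efficacy cohort (2.3) leaves out ineligible patients, those who never started treatment, and "patients that are lost to follow-up before their first response evaluation (by RECIST 1.1". It has no exclusion for patients who were still being followed but had too little possible follow-up.

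**The concern.** A proportion at a fixed time is sound when every patient in the denominator could have been observed to that time. The closure removes that guarantee for anyone enrolled late. Such a patient, if treated, progression-free and stable at the cut-off, is not ineligible, untreated or lost to follow-up, and so remains in the denominator. Disease stabilisation at 24 weeks cannot be shown for that patient, so the patient cannot enter the numerator.

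Nothing else in the SAP repairs this. PFS, OS and time to treatment failure have censoring rules; the disease control rate has none. Section 5.2 covers baseline values, dates and PFS without assessments, but not an unreached week 24. The ITT repeat in 4.3.4 uses a cohort at least as large and keeps the same patients. Section 3 does adapt the formal response test to the closure, but the disease control denominator was carried over unchanged.

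At stake is a named secondary endpoint whose value would depend partly on when patients happened to be enrolled. The logistic models in 4.3.1 and the Fisher tests in 4.3.6 would inherit the same classification.

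**Working it through.** **Inputs from the SAP**
- Denominator: whole analysis cohort (2.2.2), here the efficacy cohort (4.3.1).
- End of follow-up: 31 March 2021 (2.1). Outstanding data due: 28 February 2021 (5.1).
- Activation: April 2018 (2.1), taken as 1 April. Closure announced: 8 February 2021 (5.1).
- Planned accrual: about 1 patient per month, with a 6-month start-up (1.6).
- Week 0 is treatment start, ideally within 7 days of enrolment (1.4).
- Response rates of 15% and 35% (1.5), borrowed below for an early-response share.

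**Not in the SAP, so assumed:** cohort size N, the number k whose week 24 falls after the cut-off, and the true 24-week rate p (0.30 and 0.50 used). Late enrollees are assumed to have the same underlying rate as the others.

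**The plan's own figure.** The SAP gives no design figure for disease control. Its only one, for response (n = 41, at least 12 responders), reproduces: exact binomial alpha 0.0147 (stated 0.015) and power 0.824 (stated 0.82). It does not bear on this point.

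**Step 1: latest enrolment date that allows 24 weeks (168 days)**

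| Governing cut-off | Week 24 counted from enrolment | Counted from treatment start 7 days after enrolment |
|---|---|---|
| 31 March 2021 | 14 October 2020 | 7 October 2020 |
| 28 February 2021 | 13 September 2020 | 6 September 2020 |

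The date depends on two choices that the SAP leaves open for this endpoint.

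**Step 2: size of the effect.** If none of the k patients can be counted as controlled, the expected rate is p(N − k)/N. The bias is −p·k/N, a relative underestimate of k/N.

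| N | k | k/N | Rate at p = 0.50 (bias) | Rate at p = 0.30 (bias) |
|---|---|---|---|---|
| any | 0 | 0% | 50% (0) | 30% (0) |
| 28 | 1 | 3.6% | 48.2% (−1.8 points) | 28.9% (−1.1) |
| 28 | 2 | 7.1% | 46.4% (−3.6) | 27.9% (−2.1) |
| 28 | 4 | 14.3% | 42.9% (−7.1) | 25.7% (−4.3) |
| 15 | 2 | 13.3% | 43.3% (−6.7) | 26.0% (−4.0) |

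**Step 3: a coherent range for k/N.** If accrual were uniform up to the announcement, the rate cancels and k/N is the late window divided by the accrual period.
- Window from 14 October 2020 to 8 February 2021: 117 days = 3.84 months. Accrual period: 34.3 months, or 28.3 after the start-up. So k/N = 3.84/34.3 = 11.2% to 3.84/28.3 = 13.6%.
- Window from 13 September 2020: 148 days = 4.86 months. So k/N = 4.86/34.3 = 14.2% to 4.86/28.3 = 17.2%.
- If enrolment had stopped before the window, k/N = 0.

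At the planned rate, 28.3 months give N of about 28 and 3.84 months give k of about 4. If N was 15, accrual was slower and k is about 2 (15 × 11.2% to 13.6% = 1.7 to 2.0).

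**Step 4: if a response before week 24 is enough.** Let a late patient already count with probability q. The expected rate is [p(N − k) + qk]/N. At p = 0.50, N = 28, k = 4: q = 0.15 gives 45.0% (bias −5.0 points) and q = 0.35 gives 47.9% (−2.1 points). The bias shrinks but does not vanish, because ongoing stable disease still cannot qualify.

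**Step 5: after the fix.** With numerator and denominator both limited to patients whose week-24 date falls on or before the cut-off, the expected rate is p, with no truncation bias.

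**The case against.** The strongest reply is that no bias has been shown. The SAP gives no enrolment dates, no final N and no date on which enrolment stopped, so k may be 0. It also nowhere says that a patient without a week-24 status is a failure; that is inferred from the fixed denominator. Both statements are right. They make the bias conditional, but they do not supply the missing rule.

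Second, the wording in 1.2, and one reading of 2.2.2 in which the 24 weeks attach only to stabilisation, would let a late-enrolled responder count at once. This stands, and it reduces the effect to patients with ongoing stable disease. Late enrollees who progressed or died before the cut-off are true failures on any reading.

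Third, section 4.3.2 already plans a Kaplan-Meier 6-month PFS estimate in the same cohort, which handles administrative censoring at nearly the same time. Disease control has no threshold or test against a null, its regressions are planned only if feasible, and its subgroups are exploratory. This limits the consequence, but the reported disease control rate and its interval remain uncorrected.

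A reader might also infer that the response rate suffers in the same way, through treated patients whose first scan was not yet due at closure. The SAP does not support that: it states no tumour-assessment schedule, and a patient enrolled on the announcement date still had 51 days to 31 March 2021.

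**Conclusion.** The point holds as a missing rule with a conditional bias. As written, the denominator can only pull the 24-week disease control rate downward when some patients could not reach week 24 by the cut-off. The expected relative shortfall is at most k/N, less if an earlier response suffices, and zero if k = 0. Under uniform accrual up to the announcement, k/N would be about 11% to 17%. At an assumed true rate of 50% that is about 6 to 9 points (0.50 × 11.2% to 0.50 × 17.2%). These figures rest on assumed accrual and on late enrollees having the same underlying rate.

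A reader might conclude that the reported rate is biased, or that everyone enrolled after 14 October 2020 was recorded as a failure. The SAP supports neither: it shows no such enrolment, and that date holds only if week 24 runs from enrolment and 31 March 2021 governs tumour assessments.

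**What to change.** In 2.2.2 and 4.3.1:
- State the origin of week 24 (enrolment or treatment start) and the data cut-off that governs tumour assessments (31 March or 28 February 2021). Derive the eligibility date from these rather than fixing a calendar date.
- Estimate the 24-week disease control rate among efficacy-cohort patients whose week-24 date falls on or before that cut-off, whatever their outcome. Select on this potential follow-up, not on having a week-24 assessment. Dropping only unassessed patients would remove those still controlled, keep late enrollees who had failed early, and still bias the rate downward.
- Report the whole-cohort rate as a worst-case sensitivity analysis, and state how many patients the closure left unassessable.
- Align the definitions in 1.2 and 2.2.2 on whether a response before week 24 is enough.

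The cost is a few sentences and one extra table row. The downside is a few fewer patients in the main estimate and a slightly wider interval. If no patient is affected, the result is unchanged.

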## 2.2.3 Exploratory endpoints

Other endpoints that will be presented, in an exploratory frame, include:

- Time to treatment failure (TTF) is defined as time from the date of enrolment until discontinuation of protocol treatment for any reason (including progression of disease, death, treatment discontinuation due to any reason, such as treatment toxicity or investigator's decision, withdrawal/lost to follow-up (LFU)). Censoring for TTF (patients on treatment) will occur at the last follow-up date.

Correlative endpoints include:

- Type of RET fusion and other transcripts

Co-mutations detected with either Next Generation Sequencing (NGS), or Copy Number Variations. Correlative endpoints will be used in the subgroup analysis.

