#### 4.2 Follow-up information and treatment administration

Firstly, a consort flow diagram will be created.

Median follow-up (FU) of the patients along with the respective interquartile range (IQR) and the number (%) of patients that are still alive, will be summarized in a table. Median follow-up time will be estimated based on the method of reverse censoring of OS. A Kaplan-Meier plot will be provided for illustrative reason.

Treatment information will be summarized and presented in a tabular format. More specifically:

- The number of patients that started treatment will be reported. For those patients enrolled, progressed but with physician's and their own agreement continued receiving treatment, information on treatment failure after first progression will be additionally provided.
- The number of patients that did not receive any dose of trial treatment, along with reasons for not doing so will also be presented.
- Number of treatment failures, the 6-month TTF estimate and median TTF time along with the corresponding 95% CIs and the reasons for treatment failure/discontinuation will be presented.
- TTF will be graphically depicted via a Kaplan Meier plot.
- For patients with treatment failure, information for further lines of treatment will also be provided.

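### The TTF rule has no exception for stops caused by the trial's own closure, so any patient taken off protocol treatment solely for that reason would count as a treatment failure

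*SAP*

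**What the plan says.** SAP section 2.2.3 defines TTF, an exploratory endpoint, as time from enrolment "until discontinuation of protocol treatment for any reason". The bracket that follows lists progression, death, toxicity, investigator's decision, withdrawal and loss to follow-up as examples. It neither names closure of the trial nor excludes it. The only censoring rule is: "Censoring for TTF (patients on treatment) will occur at the last follow-up date".

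Section 2.1 records that "ETOP decided to prematurely close the ALERT-lung trial, by March 31, 2021", because new agents had become available and an external study had shown only moderate activity. Section 5.1 adds: "On February 8, 2021, ETOP announced the premature closure of the ALERT-lung trial". Section 2.1 also states: "Follow-up and safety information will be updated until 31 March 2021". Section 5.1 puts database lock and trial closure on that same date.

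Section 4.2 will report "Number of treatment failures, the 6-month TTF estimate and median TTF time", with 95% confidence intervals, a Kaplan-Meier plot and the reasons for failure or discontinuation.

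**The concern.** A stop imposed by the sponsor for reasons external to the patient carries no information about whether alectinib was failing in that patient. The definition still makes it an event. A patient who has been taken off protocol treatment is no longer on treatment, so the censoring sentence does not apply, and the catch-all wording does.

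The patients exposed to this are those still on drug when closure was announced, who are likely to include those doing best. Counting them as failures would understate time on treatment and add administrative stops to the number of treatment failures. The SAP did adapt to closure elsewhere: section 3 replaces the formal test of the response rate for that reason. The TTF definition was not revisited. Section 5 has a second statistician independently reproduce all analyses, and without an explicit rule two careful analysts could code the same patient differently.

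**Working it through.** The SAP states no TTF figure, so there is none to reproduce. The check has two parts: what the text implies, and how large the effect could be.

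**Reading the text.** Three kinds of patient need a rule at closure.

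1. Stopped earlier for progression, toxicity, withdrawal and so on: an event. No dispute.
2. Still on protocol treatment at the 31 March 2021 cut-off: censored at last follow-up.
3. Taken off protocol treatment between 8 February and 31 March 2021 (20 + 31 = 51 days) solely because of the closure: an event on the literal wording, with no exception anywhere in the SAP.

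Only the third group is affected. Changing a censored time to an event at the same time can never raise a Kaplan-Meier curve, so the direction is fixed. The failure count rises by one for each such patient.

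**Upper bound on size.** The SAP gives no TTF rate, enrolled number, date of last enrolment or count on drug at closure. The following are therefore assumptions: exponential TTF with true median *m* of 4, 6 or 9 months; uniform entry over *A* months, ending *g* months before closure; and every patient on drug at closure stopped because of it and counted as a failure. The last assumption makes this a ceiling, because it leaves nobody for the existing censoring rule.

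- With closure stops censored, the curve is S(t) = 2^(−t/m).
- With closure stops as events, it is S*(t) = S(t) × G(t), where G(t) is the probability that entry was more than t months before closure: G(t) = min{1, (A + g − t)/A}.
- The fall at 6 months is S(6) × [1 − G(6)]. The new median solves S*(t) = 0.5.

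Activation in April 2018 (section 2.1) and closure at the end of March 2021 give A + g = 36 months for the first three settings. The fourth is the most extreme: 30 months of entry running right up to closure.

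| Entry ends before closure | G(6) | m | 6-month TTF, censored → event | Median, censored → event |
|---|---|---|---|---|
| 12 months (A = 24) | 1 | 4, 6, 9 | no change | no change |
| 6 months (A = 30) | 1 | 4, 6 | no change | no change |
| 6 months (A = 30) | 1 | 9 | no change | 9.0 → 8.1 |
| 2 months (A = 34) | 30/34 = 0.882 | 4 | 0.354 → 0.312 | 4.0 → 3.7 |
| 2 months (A = 34) | 0.882 | 6 | 0.500 → 0.441 | 6.0 → 5.2 |
| 2 months (A = 34) | 0.882 | 9 | 0.630 → 0.556 | 9.0 → 7.0 |
| 0 months (A = 30) | 24/30 = 0.800 | 4 | 0.354 → 0.283 | 4.0 → 3.3 |
| 0 months (A = 30) | 0.800 | 6 | 0.500 → 0.400 | 6.0 → 4.6 |
| 0 months (A = 30) | 0.800 | 9 | 0.630 → 0.504 | 9.0 → 6.1 |

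**Check by simulation.** In the 36-month settings, 2,000 simulated trials per setting, each analysed both ways, agree with the formula. For N = 41, entry ending 2 months before closure and m = 6, the median goes from 6.0 to 5.1 and 6-month TTF from 0.50 to 0.44. For N = 14 and m = 9, the sample median goes from 8.7 to 6.3, a fall of 2.4 months, and 6-month TTF from 0.63 to 0.56. With entry ending 12 months before closure, neither summary moved at either sample size.

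**The case against.** The strongest reply is that the SAP already deals with the main case. Patients on treatment are censored, and follow-up, lock and closure share one date, so a patient still taking alectinib at the cut-off is handled correctly. Nothing in the SAP says that anyone's drug was stopped because of the closure. How ongoing patients were to be managed may well be set out in the closure guidance letter cited in section 5.1, which is not available here. Section 4.2 already calls for reasons for discontinuation, so a reader could see how many events were administrative. TTF is exploratory, is reported with treatment administration, and is absent from the efficacy endpoints re-assessed in section 4.3.4.

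Most of this stands, and it limits the point. A reader might infer from the definition that closure did turn patients into failures and that the reported TTF is biased downward. The SAP does not support that, because both statements depend on at least one patient having been stopped solely for closure before the cut-off. Nor can the larger falls in the table be read as expected effects: they treat every patient on drug at closure as a failure, and the larger ones also need entry close to closure.

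What the reply does not remove is the rule itself. For a patient in the third group the wording leads to an event. A table of reasons would reveal this, but it would not correct the failure count, the median, the 6-month estimate or the plotted curve.

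**Conclusion.** The point holds in conditional form and is minor. As written, any patient taken off protocol treatment solely because of the closure, between the announcement and the cut-off, would be a TTF failure. The only possible direction is more failures and a lower curve.

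The size cannot be determined from the SAP. It is zero if nobody stopped for this reason. Even if some did, the 6-month estimate is unchanged when all of them had entered at least 6 months before stopping, and the median need not move when enrolment ended well before closure. Under the ceiling assumptions, the fall in the median reaches about 2 to 3 months at a true median of 9. The fall in the 6-month estimate is 4 to 7 percentage points with entry ending 2 months before closure. It is about 10 points (7 to 13 across the true medians tried) with entry running right up to closure.

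The primary response analysis and the definitions of disease control, PFS and OS are not touched.

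**What to change.** Add one sentence to section 2.2.3: discontinuation solely because of the premature closure of the trial is not a TTF event, and such patients are censored at the date of last protocol treatment. The word solely matters. A patient who also had progression, toxicity or another listed reason remains an event.

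In the section 4.2 table of reasons, show closure as its own row, outside the count of treatment failures. If the sponsor prefers to keep closure stops as events, the report should state their number and give a sensitivity analysis with them censored.

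The cost is a sentence and a table row. Reasons for discontinuation are already to be reported, so no new data should be needed, provided closure can be distinguished among the recorded reasons. The rule should be fixed before the TTF analysis is run.
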